The SAP was written in accordance with the recommendations outlined in the International Conference on Harmonisation (ICH) E9 Guideline entitled "Guidance for Industry: Statistical Principles for Clinical Trials" and the ICH-E3 Guideline entitled "Guidance for Industry: Structure and Content of Clinical Study Reports".

1.1.1 Study Design

This is a phase 2, multicenter, randomized, dose-ranging, double-blind, placebo-controlled, United States (US) study to assess the efficacy, safety, and duration of response of abobotulinumtoxinA for the treatment of moderate to severe platysmal bands.

After undergoing a screening visit, enrolled subjects will receive a single treatment of abobotulinumtoxinA or placebo at baseline. The planned clinical study duration (from first subject first visit to last subject last visit) is approximately 21.5 months.

1.1.2 Number of Subjects and Randomization

The study is planned to enroll approximately 240 subjects who will be treated with abobotulinumtoxinA (approximately 60 subjects/dose) or placebo (up to 60 subjects depending on the number of dose groups that will run in the study).

Initially, eligible subjects will be randomly assigned at baseline to the following treatment

Study Objectives 1.2

[figure not shown]
The objectives of the study are to evaluate the safety and efficacy of a single dose of of abobotulinumtoxinA compared to placebo in the treatment of moderate to severe platysmal bands.

GALDERMA Title 43USD1804 Statistical analysis plan	Doc id
---	--------

1.2.1 Primary Efficacy Objective

The primary objective is to evaluate the efficacy of a single dose of abobotulinumtoxinA, respectively, compared to placebo in the treatment of moderate to severe platysmal bands using the Investigator Live Assessment (ILA) Photographic Scale at maximum contraction at Month 1.

1.2.2 Secondary Efficacy Objectives

[figure not shown]
Safety Objectives 1.2.4

[figure not shown]
The safety objective is to evaluate the effect on safety endpoints of a single dose of abobotulinumtoxinA and placebo in the treatment of platysmal bands.

Doc id 43USD1804 Statistical analysis plan - GALDERMA

[figure not shown]
Efficacy Assessments 1.3

For all assessments, baseline will be defined as the observation that is closest to but prior to study treatment on Day 0. Likewise, change from baseline will be calculated as the value at a given time point minus the baseline value.

1.5 Safety Assessments

Effective date: 2019-12-23 06:09

Effective

Version: 1.0

The methods for collecting safety data are described in Section 7.2 of the Clinical Study Protocol.

1.6 Safety Endpoints

Safety endpoints include:

(i) Treatment Emergent Adverse Events (TEAEs)

Adverse events (AEs) are to be monitored throughout the course of the study. The study period for the purpose of AE collection is defined as the period from the signing of a study specific informed consent to study exit for a subject. AEs recorded on the electronic case report forms (eCRFs) will be coded using the Medical Dictionary for Regulatory Activities (MedDRA). AEs will be classified as treatment-emergent adverse events (TEAEs) if the AE had an onset time greater than or equal to the time of the dose of study treatment.

Adverse events endpoints include:

- Incidence,
- Causality (related/not related to investigational product or protocol procedure),
- Intensity (mild/moderate/severe),
- Time to onset,
- Duration,
- Leading to study withdrawal,
- Seriousness.

(ii) Focused Physical Examination

At all visits the Investigator or designee will perform a physical examination of the subject that includes the face, head, and neck. The Investigator may choose to investigate any other sign that he/she observes during the physical examination and should assess all abnormal findings for clinical significance.

(iii) Vital Signs

Vital signs (including blood pressure, heart rate, and respiratory rate) will be evaluated at the baseline visit (pre and post-treatment), and at each study visit thereafter through the termination visit.

Vital signs endpoints include:

- Values,
- Changes from baseline.

All abnormal values at the screening visit identified as clinically significant by the Investigator will be recorded in the medical history.

For any clinically significant changes from the screening visit, an AE is to be recorded.

Normal ranges checks, as programmed in the eCRF to alert the investigator to assess clinical significance for values outside of these ranges, are shown in Table 4 below.

Title
43USD1804 Statistical analysis plan Doc id GALDERMA

Table 4. Vital Sign Normal Ranges

Measure	Normal Range
Sitting Systolic blood pressure	90-150 mmHg
Sitting Diastolic blood pressure	60-90 mmHg
Sitting Heart rate	50-100 beats/min
Sitting Respiratory rate	12-24 breaths/min

(iv) **Jawline and Oral Commissure Safety Assessment**

To determine if treatment with abobotulinumtoxinA or placebo of the platysmal bands adversely affects the subject's jawline or oral commissures, the Investigator will assess these areas relative to the subject's pre-treatment appearance

2 **Statistical Methods**

2.1 **General Methods**

If any SAP changes are needed before database lock (DBL), the SAP will be amended. Changes after DBL will be documented in the Clinical Study Report (CSR). If additional supportive or exploratory analyses are requested after SAP approval, this will not require amendment of the SAP, but these additional analyses will be described in the CSR.

Some of the analyses detailed here may be more explicit or in some respects different from those stated in the protocol. In case of differences, this SAP supersedes the statistical sections in the protocol.

2.1.1 **Programming Conventions**

EMB Statistical Solutions will have responsibility for performing analyses. All computations for statistical analyses will be performed using SAS® software, Version 9.4 or later. All SAS programs used in the production of statistical summary outputs will be validated with independent programming prior to finalization. In addition, all program outputs will be independently reviewed. The validation process will be used to confirm that all data manipulations and calculations were accurately done. Once validation is complete, a senior statistical reviewer will perform a final review of the documents to ensure the accuracy and consistency with this plan and consistency within tables. Upon completion of validation and quality review procedures, all documentation will be collected and filed by the project statistician or designee.

The eCRF data for all subjects will be provided in Standard Data Tabulation Model (SDTM) datasets. Analysis Data Model (ADaM) datasets will be developed from the SDTM datasets for use in table and figure production.

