7.2.5.1 Definitions

7.2.5.1.1 Adverse Events (AE)

According to ICH E2A, an AE is any untoward medical occurrence in a patient or a clinical investigation subject administered a pharmaceutical product and which does not necessarily have a causal relationship with this treatment. An AE can therefore be any unfavorable and unintended sign (including an abnormal laboratory finding), symptom, or disease temporally associated with the use of a medicinal (investigational) product, whether or not related to the medicinal (investigational) product.

Thus any new sign, symptom or disease, or any clinically significant worsening of an existing sign, symptom or disease (including new episodes of a chronic disease [e.g., hay fever, allergy]) compared to the condition at the first visit, should be considered as an AE. Lack of efficacy is not considered as an AE.

Notes:

- There should be an attempt to report a diagnosis rather than the signs, symptoms or abnormal laboratory values associated with the report of an AE. However, a diagnosis should be reported only if, in the investigator's judgment, it is relatively certain. Otherwise, symptoms, signs, or laboratory values should be used to describe the AE.
- Pregnancy is not to be considered as an AE; however, is a special situation that must be monitored as described in Section 7.2.5.2.4.

[REDACTED]

Effective

Version: 6.0

Effective date: 2019-08-09 13:21

7.2.5.1.2 *Treatment Emergent Adverse Event (TEAE)*

A TEAE is an event that emerges during treatment, having been absent pre-treatment, or worsens relative to the pretreatment state.

Investigators are responsible for monitoring, recording, and reporting all AEs that occur during the study as described. TEAEs will be delineated from AEs following database lock.

7.2.5.1.3 *Serious Adverse Events (SAE)*

A SAE is any untoward medical occurrence that at any dose:

- Results in death,
- Is life-threatening,
- Requires inpatient hospitalization or prolongation of existing hospitalization,
- Results in persistent or significant disability/incapacity, or
- Is a congenital anomaly/birth defect.

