The Investigator is to classify the intensity of AEs using the following definitions as a guideline. For this classification, the Investigator will take into account the possible range of the intensity of the event and report the grade of intensity which is the most appropriate according to his/her medical judgment.

Mild	Awareness of signs or symptom, but easily tolerated.
Moderate	Discomfort, enough to cause interference with usual activity.
Severe	Incapacitating with inability to work or perform usual activity.

7.2.5.1.7 *Relationship to the Study Product and/or Clinical Study Procedure*

The Investigator is to determine whether there is a reasonable causal relationship between the occurrence of the AE and exposure to the study product and/or clinical study procedure.

Medical judgment should be used to determine the relationship, considering all relevant factors including the pattern of reaction, temporal relationships, relevant medical history, and confounding factors such as co-medication or concurrent diseases.

The expression “reasonable causal relationship” is meant to convey in general that there are facts or arguments to suggest a causal relationship (ICH E2A, Section IIIA 1).

The relationship assessment for an AE is to be completed using the following definitions as a guideline:

Reasonable Possibility:

According to the reporting Investigator, there is a reasonable possibility (i.e., suggestive evidence or arguments) that there is a causal relationship irrespective of the dose administered between:

- The study product (active or placebo) and the AE.
- The clinical study protocol procedure (e.g., bruising or marks from blood draws, injection related trauma, etc.) and the AE.

A two-point scale (Yes or No response) shall be used for the causality assessment. The Investigator shall be asked to indicate a response to each of the following questions in the eCRF:

Effective date: 2019-08-09 13:21

Effective

Version: 6.0

- “Do you consider that there is a reasonable possibility that the event may have been caused by the study product?”, and
- “Do you consider that there is a reasonable possibility that the event may have been caused by the study product injection procedure?”

If any of these questions is answered Yes, the AE is considered related.

No Reasonable Possibility:

No suggestive evidence or arguments can be identified regarding a causal relationship between the study product or the clinical study protocol procedure and the AE.

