7.2.5.2 Reporting Procedures

7.2.5.2.1 Procedure for Reporting Adverse Events

The collection of AEs is from the time that a subject signs the ICF to their final visit.

At each post-enrollment visit, the Investigator (or sub-Investigator) will question the subject about AEs using an open non-persuasive question to elicit reporting of AEs, for example “Have you noticed any change in your health since the last visit?” Directed questioning and examination will then be performed as appropriate.

Any AE occurring during the AE reporting period, whether it is related to the study product or not, will be recorded immediately in the source document, and described on the AE form of the eCRF along with the date of onset, severity, relationship to the study product, action taken and outcome, without omitting any requested and known information. Additional information may be requested under certain circumstances.

Adverse Events (AEs) assessed as related to the treatment or study procedure will be monitored until they have resolved or reached a stable condition. Other AEs will be monitored until the last visit if they have not resolved or reached a stable condition.

The Investigator will obtain and maintain in the subject’s files all pertinent medical records, information and medical judgment from colleagues who assisted in the treatment and follow-up of the subject. If necessary, the Investigator will contact the subject’s personal physician or hospital staff to obtain further details.

For SAEs (see Section 7.2.5.2.3) and pregnancies (see Section 7.2.5.2.4), the Sponsor is to be informed immediately. The event must be reported by e-mail to the Safety email within 24 hours of receipt of the information (contact details in Section 7.2.5.2.3).

7.2.5.2.2 Procedure for Reporting an Adverse Event that may indicate remote spread of toxin effect or a hypersensitivity reaction

Adverse events that may indicate remote spread of toxin or hypersensitivity reactions (Appendix 6) should be reported to the Safety email [redacted] within 24 hours of awareness using the AE Clarification Form.

Effective date: 2019-08-09 13:21

In case of difficulty to obtain all the required information within 24 hours, an initial report can be submitted with follow up information provided within 24 hours of awareness of the new information.

The following information should be provided on the AE Clarification Form:

- Subject identification (subject number and initials)

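### SAP 1.6(i) defines TEAEs by onset time alone and drops the protocol's worsening limb, which matters in one narrow case: a pre-dose AE that worsens after injection on the same record

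*SAP*

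**What the plan says.** The SAP's rule is in 1.6(i): an AE is a TEAE "if the AE had an onset time greater than or equal to the time of the dose of study treatment". SAP 2.5.2 and 2.5.3 use the term without redefining it.

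The protocol's rule is in 7.2.5.1.2: "A TEAE is an event that emerges during treatment, having been absent pre-treatment, or worsens relative to the pretreatment state". The same section adds: "TEAEs will be delineated from AEs following database lock". That defers the sorting of events but leaves the definition as it stands.

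Pre-dose AE records can exist, because under Protocol 7.2.5.2.1 "The collection of AEs is from the time that a subject signs the ICF to their final visit".

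SAP 2.1 says that where the two documents differ, the SAP prevails over the protocol's statistical sections. The TEAE definition is in Protocol Section 7 (assessments); statistical methods are in Section 9.

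**The concern.** Incidence and severity of TEAEs is the first-listed safety endpoint in Protocol 2.1.4, and most AE tables in SAP 2.5.2 are built on the TEAE flag. The protocol defines that flag with two limbs and the SAP with one. No visible SAP text acknowledges or explains the change, and the precedence clause does not plainly reach a definition outside the statistical sections.

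What is at stake is whether entries in the TEAE tables follow the protocol's definition, or depend on whether a site opens a new record or updates an old one when an event worsens.

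**Working it through.** No sample size, power or error rate is involved, and the plan gives no figure to reproduce. The check applies both definitions to each possible AE history, then counts the tables affected.

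**Step 1. Classification under each rule**

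| AE history | Protocol 7.2.5.1.2 | SAP 1.6(i) |
|---|---|---|
| New event after injection | TEAE | TEAE |
| Medical-history condition worsens after injection, entered as a new AE with post-dose onset | TEAE | TEAE |
| Onset between consent and injection, no worsening | not a TEAE | not a TEAE |
| Onset between consent and injection, worsens after injection, entered as a new record with post-dose onset | TEAE | TEAE |
| Onset between consent and injection, worsens after injection, kept on the same record | TEAE | not a TEAE |

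Only the last row differs.

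**Step 2. Can the last row arise?** The visible text permits it but does not require it.

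- Protocol 7.2.5.1.1 treats as an AE "any clinically significant worsening of an existing sign, symptom or disease", "compared to the condition at the first visit, should be considered as an AE". The reference point is the first visit, not the injection, and no visible sentence says that worsening of an AE already on file opens a new record.
- Protocol 7.2.5.1.6 asks the investigator to "take into account the possible range of the intensity of the event and report the grade of intensity which is the most appropriate". That is compatible with one record and one grade for an event whose intensity changes.
- Protocol 7.2.5.2.1 has related AEs followed to resolution or stability, and for the rest: "Other AEs will be monitored until the last visit if they have not resolved or reached a stable condition". That too is compatible with one continuing record.
- SAP 1.5 refers to Protocol 7.2 for data collection, so the SAP adds no recording rule of its own there.

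**Step 3. Tables affected (SAP 2.5.2)**

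The overall summary has 6 items: 1 on any AE and 5 on TEAEs. The SOC/PT breakdowns number 7, all on TEAEs.

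- Event that is unrelated, non-serious and does not lead to discontinuation: missing from 2 of 6 summary items (any TEAE; TEAE by intensity) and 4 of 7 breakdowns (all, maximum intensity, causality, intensity with causality).
- Each of related, serious and leading to discontinuation adds one item and one breakdown. With all three: 2 + 3 = 5 of 6, and 4 + 3 = 7 of 7.

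The event remains in the any-AE item and the listings. If judged related, it also remains in the summary of days to onset and duration, which SAP 2.5.2 builds on related AEs rather than related TEAEs. Time to onset there is start date minus treatment date, so an event that began on an earlier day would show a negative value while being absent from the related-TEAE table.

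**Step 4. Scale of one subject**

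Denominators come from Protocol 5.1 (60 active and 20 placebo per treatment group) and SAP 1.1.2 (up to 60 placebo, depending on how many dose groups run).

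- Dose group: 1/60 = 1.67 percentage points.
- Pooled placebo: 1/60 = 1.67, 1/40 = 2.50 or 1/20 = 5.00 points if three, two or one dose groups run.

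These are the weight of one subject in a table, not an estimate of the effect. Overall TEAE incidence moves only if that subject has no other TEAE. No event rate is assumed.

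**The case against.** The best answer is that the protocol's own AE rules already handle most worsening. An event absent at the first visit, present before injection and worse afterwards is still worse than at the first visit. On an ordinary reading the worsening is then an AE in its own right, with a post-dose onset that the SAP rule would catch. Protocol 7.2.2 makes clinically significant examination findings at screening or baseline exclusionary. Other pre-treatment findings go to medical history, and clinically significant changes from baseline become AEs. Protocol 7.2.3 treats vital signs in a similar way. Text is also blacked out within 7.2.5, where a recording rule could sit. All of this stands and makes the exposed set small. It does not close the gap, because no visible sentence requires a new record and the two definitions, both visible in full, still differ.

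A reader might infer three stronger things that the documents do not support.

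- *That every affected event vanishes from five summary items and all seven breakdowns.* That is a ceiling, reached only by an event that is related, serious and leads to discontinuation.
- *That AESIs would be lost.* The event would not enter the AESI search, which is limited to TEAEs. But SAP 2.5.3 also excludes cases whose onset timing does not fit the mechanism of action, or that have another clinical explanation. An event with recorded onset before injection might be excluded on either ground anyway.
- *That safety review or the comparison between arms is compromised.* Possible remote-spread and hypersensitivity events are reported and assessed under Protocol 7.2.5.2.2 whatever their TEAE status. The sponsor monitors all AEs (Protocol 9.1.3.1) and the DSMC reviews the AE list. Safety analysis is descriptive (SAP 2.5), and the same rule applies to placebo.

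**Conclusion.** The inconsistency is real, and its severity is minor. As written, the SAP rule excludes an event that the protocol counts when an AE begins between consent and injection, worsens after injection and stays on one record.

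That the definitions differ is certain from the text. The practical effect is not: it assumes that such events occur and that sites keep them on one record. The number cannot be estimated from the documents and is probably small. It would be zero if a redacted recording rule, or site practice, already splits such events.

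**What to change.** Before database lock, amend SAP 1.6(i) to: *onset at or after study treatment, or onset before treatment and worsening at or after treatment relative to the pre-treatment state*. Use worsening without qualification. Restricting it to intensity would be narrower than the protocol, whose term could also cover greater frequency or an event becoming serious.

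To make the rule derivable, confirm or state that post-dose worsening of a pre-dose AE is entered as a new AE record with its own onset, or is flagged. A single grade per event would not show the change. The AESI search in SAP 2.5.3 would then draw on TEAEs under the amended definition, with its existing exclusions unchanged.

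The cost is one sentence, through the pre-lock amendment that SAP 2.1 already provides for, and one data-entry confirmation or flag. The downside is slightly higher TEAE counts and minor programming or query work on pre-dose AEs. If worsening is already entered as a new record, only the wording changes.

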2.1.2 Reporting Conventions

The formats for the tables, listings, and figures described in this SAP will be provided in a companion document. Changes to the formats of these reports that are decided after the finalization of the SAP will not require an amendment. In addition, any additional supportive or exploratory analyses requested after SAP approval will not require amendment of the SAP. These additional analyses will be described in the CSR.

All study data from the eCRFs as well as derived variables will be provided in subject data listings. An indication of specific listings for each data type will not be indicated in the text of subsequent SAP sections. Data listings supplied as part of the CSR will be sorted by treatment group, study center number concatenated with subject number, assessment dates, and/or time point.

The following conventions will be applied to all data presentations and analyses:

- Placebo-treated subjects will be pooled together in summary tables and for analyses.
- Treatment groups to be summarized include abobotulinumtoxinA and pooled placebo.
- Quantitative variables will generally be summarized by the number of subjects, mean, standard deviation, median, minimum, and maximum. Unless otherwise specified, the minimum and maximum values will be displayed to the same number of decimal places as the raw data, the mean and median will be presented to one extra decimal place compared to

GALDERMA

Title

43USD1804 Statistical analysis plan -

the raw data, and the standard deviation will be displayed to two extra decimal places compared to the raw data.

- Categorical variables will be summarized by the number and percentage of subjects within each category. Unless otherwise specified, the percentage will be presented in parentheses to one decimal place. Frequency and percentage values of 0 will be presented as '0' rather than '0 (0)'.
- All summary tables will include the analysis population sample size (i.e., number of subjects) in each treatment group.
- Date variables will be formatted as DDMMMYYYY for presentation.

